7.2.2.5 Clinical Laboratory Evaluations

All clinical laboratory assays will be performed according to the laboratory's normal procedures. Reference ranges are to be supplied by the laboratory and will be used to assess the clinical laboratory data for clinical significance and out-of-range pathological changes. The investigator should assess out-of-range clinical laboratory values for clinical significance, indicating if the value(s) is/are not clinically significant or clinically significant. Abnormal clinical laboratory values, which are unexpected or not explained by the subject's clinical condition, may, at the discretion of the investigator or sponsor, be repeated as soon as possible until confirmed, explained, or resolved.

The following clinical laboratory assessments will be performed:

BIOCHEMISTRY

Blood samples (8.5 mL) for serum biochemistry will be collected into a red top gel separator tube at the time points described in [Table 1](#), [Table 2](#) and [Table 3](#). The following parameters will be assessed:

| | | |
|---|-------------------------------------|---------------------------|
| Sodium | Phosphorus | β -hCG ^b |
| Potassium | Total protein | Magnesium |
| Glucose | Total CO ₂ (Bicarbonate) | PTH ^c |
| Blood urea nitrogen | Albumin | FSH ^b |
| Creatinine | Aspartate transaminase | |
| Calcium | Alanine transaminase | |
| Chloride | Gamma glutamyl transferase | |
| Thyroid stimulating hormone (TSH) ^a | Alkaline phosphatase | |
| Thyroxine (T ₄ total) ^a | Total bilirubin | |
| Triiodothyronine (T ₃) ^a | Uric acid | |

CO₂=carbon dioxide; FSH=follicle stimulating hormone; T₃=triiodothyronine; T₄=thyroxine; TSH=thyroid stimulating hormone

^a See [Table 1](#), [Table 2](#), and [Table 3](#).

^b Females only.

^c Parathyroid hormone at screening and Day -1 is for baseline eligibility use only and not for PK analysis.

HEMATOLOGY

Blood samples (4mL) for hematology will be collected into a K₂-EDTA (ethylenediaminetetraacetic acid) tube at the time points described in [Table 1](#), [Table 2](#), and [Table 3](#). The following parameters will be assessed:

| | |
|--|------------------------------|
| Hemoglobin | Total neutrophils (absolute) |
| Hematocrit | Eosinophils (absolute) |
| Red blood cells | Monocytes (absolute) |
| Platelet count | Basophils (absolute) |
| White blood cell count; total and differential | Lymphocytes (absolute) |

URINALYSIS

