11.2 Clinical Laboratory Variables

Descriptive statistics for clinical laboratory values (in SI units) and changes from baseline at each assessment time point as well as shift tables from baseline to each visit for quantitative variables will be presented by ethnic group and dose for the following clinical laboratory variables.

Hematology Hemoglobin, hematocrit, red blood cells (RBC), platelet count, white blood cell count – total and differential (WBC), total neutrophils (absolute), eosinophils (absolute), monocytes (absolute), basophils (absolute), lymphocytes (absolute).

Biochemistry Sodium, phosphorus, β -hCG^b, potassium, total protein, magnesium, glucose, total CO₂ (Bicarbonate), PTH^c, blood urea nitrogen, albumin, FSH^b, creatinine, aspartate transaminase (AST), calcium, alanine transaminase (ALT), chloride, gamma glutamyl transferase (GGT), thyroid stimulating hormone (TSH)^a, alkaline phosphatase (ALP), thyroxine (T₄ total)^a, total bilirubin, triiodothyronine (T₃)^a, uric acid.

CO₂=carbon dioxide; FSH=follicle stimulating hormone; T₃=triiodothyronine; T₄=thyroxine; TSH=thyroid stimulating hormone

^a See Table 1, Table 2, and Table 3.

^b Females only.

^c Parathyroid hormone at screening and Day -1 is for baseline eligibility use only and not for PK analysis.

Urinalysis pH, glucose, protein, blood, ketones, bilirubin, nitrites, leukocyte esterase, specific gravity.

Clinical laboratory test values are potentially clinically important (PCI) if they meet either the low or high PCI criteria listed in Table 4. The number and percentage of subjects with post-baseline PCI values will be tabulated by ethnic group and dose. The percentages will be calculated relative to the number of subjects with available assessments at that dose level. The numerator is the total number of subjects with at least 1 post-baseline PCI value at that dose level. A supportive listing of subjects with post-baseline PCI values will be provided including the subject number, ethnic group, dose, baseline, and post-baseline values.

Listings for serum and urinary clinical laboratory results will be produced for all patients in the Safety Analysis Set. Clinically potential important test results will be listed as well.

Table 4 Criteria for Potentially Clinically Important Laboratory Tests

Parameter	Classification (on CDRs)	Criteria
Biochemistry		
Sodium	HIGH	> 5 mmol/L (5 mEq/L) above ULN
	LOW	> 5 mmol/L (5 mEq/L) below LLN

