Potassium	HIGH + INCREASE	Above ULN and increase of > 0.5 mmol/L (0.5 mEq/L) from baseline value
	LOW + DECREASE	Below LLN and decrease of > 0.5 mmol/L (0.5 mEq/L) from baseline value
Creatinine	HIGH + INCREASE	> 150 μ mol/L and increase > 30% from baseline value
BUN	HIGH	> 1.5 x ULN
Glucose (fasting)	HIGH	\geq 6.7 mmol/L
	LOW	\leq 4.2 mmol/L
Calcium	HIGH and INCREASE	Above ULN and Increase of \geq 0.25 mmol/L (1.0 mg/dL) from baseline value
	LOW and DECREASE	Below LLN and Decrease of \geq 0.25 mmol/L (1.0 mg/dL) from baseline value
Magnesium	HIGH and INCREASE	Above ULN and Increase of \geq 0.21 mmol/L (0.5 mg/dL) from baseline value
	LOW and DECREASE	Below LLN and Decrease of \geq 0.21 mmol/L (0.5 mg/dL) from baseline value
Phosphorus	HIGH	> 0.162 mmol/L (0.5 mg/dL) above ULN
	LOW	> 0.162 mmol/L (0.5 mg/dL) below LLN
Total protein	HIGH and INCREASE	Above ULN and Increase of \geq 20 g/L (2.0 g/dL) from baseline value
	LOW and DECREASE	Below LLN and Decrease of \geq 20 g/L (2.0 g/dL) from baseline value
Albumin	HIGH and INCREASE	Above ULN and Increase of \geq 10 g/L (1.0 g/dL) from baseline value
	LOW and DECREASE	Below LLN and Decrease of \geq 10 g/L (1.0 g/dL) from baseline value
Uric acid (with normal diet)	HIGH and INCREASE	Above ULN and Increase of > 0.119 mmol/L (2.0 mg/dL) from baseline value
	LOW and DECREASE	Above LLN and Decrease of > 0.119 mmol/L (2.0 mg/dL) from baseline value
ALT	HIGH	> 2 x ULN
AST	HIGH	> 2 x ULN
ALP	HIGH	> 1.5 x ULN
GGT	HIGH	> 1.5 x ULN
Total bilirubin	HIGH	> 1.5 x ULN
T4	HIGH	> 140.28 nmol/L
	LOW	< 57.92 nmol/L
T3	LOW	< 0.922 nmol/L

Table 4 Criteria for Potentially Clinically Important Laboratory Tests

Parameter	Classification (on CDRs)	Criteria
Biochemistry		
	HIGH	> 2.765 nmol/L
TSH	HIGH	>5.0 µU/L
	LOW	0.5 µU/L
Hematology		
RBC count	HIGH	>7.5 x10 ¹² /L
	LOW	<3 x10 ¹² /L
Hematocrit	LOW and DECREASE	≤0.6 x LLN and Decrease of ≥ 0.06 L/L (6.0%) from baseline value
	HIGH	>1.3 x ULN
Hemoglobin	LOW and DECREASE	< 100g/L (10g/dL) and Decrease of ≥ 20g/L (2.0 g/dL) from baseline value
	HIGH	>200 g/L (20g/dL)
WBC count	HIGH	>2xULN OR >16.0 x 10 ⁹ /L (16 x 10 ³ /µL)
	LOW	< 0.5xLLN OR < 3.0 x 10 ⁹ /L (3 x 10 ³ /µL)
Neutrophils	LOW	< 1.5 x 10 ⁹ /L (1.5 x 10 ³ µL) OR < 40%
	HIGH	> 6.2 x 10 ⁹ /L (6.2 x 10 ³ µL) OR > 70 %
Lymphocytes	HIGH	> 4.0 x 10 ⁹ /L (1.5 x 10 ³ µL) OR > 44 %
	LOW	< 0.8 x 10 ⁹ /L (0.8 x 10 ³ µL) OR < 22 %
Monocytes	HIGH	>11 %
Eosinophils	HIGH	> 0.5 x 10 ⁹ /L (> 500/µL) and > 10.0%
	LOW	NA
Basophils	HIGH	2%
	LOW	NA

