Platelet count (thrombocytes)	HIGH	>1.5 x ULN OR > 500 x 10 ⁹ /L (100 x 10 ³ /µL)
	LOW	0.6 x LLN OR < 100 x 10 ⁹ /L (100 x 10 ³ /µL)
Urinalysis		
Glucose	HIGH	≥ 1+
Blood	HIGH	≥ 2+
Bilirubin		Normally not found
Protein	HIGH	≥ 2+
Nitrite		Normally not found
Ketones	HIGH	≥ 2+
Leukocyte Esterase		Negative

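### SAP Table 4: the bracketed equivalents for platelets HIGH and lymphocytes HIGH contradict their own SI limits, and the TSH limits are printed only in µU/L

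*SAP*

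**What the plan says.** SAP 11.2 makes Table 4 the operative rule. A laboratory value is "potentially clinically important (PCI) if they meet either the low or high PCI criteria listed in Table 4", and subjects with such a value after baseline are counted by ethnic group and dose.

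The rows at issue are:

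- Platelets HIGH: ">1.5 x ULN OR > 500 x 10 ⁹ /L (100 x 10 ³ /µL"). The LOW row beneath it reads "0.6 x LLN OR < 100 x 10 ⁹ /L (100 x 10 ³ /µL").
- Lymphocytes HIGH: "> 4.0 x 10 ⁹ /L (1.5 x 10 ³ µL) OR > 44" %. The LOW row reads "< 0.8 x 10 ⁹ /L (0.8 x 10 ³ µL) OR < 22" %.
- TSH HIGH is above 5.0 µU/L and TSH LOW is 0.5 µU/L. Neither has a second unit, and in the text available the LOW row has no inequality sign.

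On units, SAP 11.2 opens with "Descriptive statistics for clinical laboratory values (in SI units) and changes from baseline". The paragraph that defines PCI values does not repeat this. SAP section 17, which lists departures from the protocol, does not mention these limits. The protocol gives no numeric normal range for the three tests; in section 7.2.2.5, "Reference ranges are to be supplied by the laboratory".

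**The concern.** Two rows of Table 4 each give two different numbers for one limit, and no sentence says which number a programmer should use. A third row gives a single number in a unit that looks wrong by a factor of 1000. These limits fix the numerators of the PCI tables by ethnic group and dose. Safety and tolerability at each dose is a secondary objective, and the tables are meant to show whether unusual laboratory values differ between doses or groups. A limit that flags nearly everyone, or flags low values as high, tells the reader nothing on that question.

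**Working it through.** **Conversion factor.** 1 L = 10^6 µL, so 1 x 10^9/L = 10^9/10^6 per µL = 1 x 10^3/µL. The factor is 1. The table uses it correctly for white cells HIGH: ">2xULN OR >16.0 x 10 ⁹ /L (16 x 10 ³ /µL").

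**The table's own equivalents.** Twenty-one bracketed equivalents in Table 4 were recomputed from their SI values, with a 5% allowance for rounding and standard factors for calcium, magnesium, phosphorus and uric acid. Nineteen reproduce. For example:

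- calcium: 0.25 mmol/L x 4.008 = 1.002 mg/dL (printed 1.0)
- phosphorus: 0.162 mmol/L x 3.0974 = 0.502 mg/dL (printed 0.5)
- platelets LOW: 100 x 1 = 100 (printed 100)

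Two do not, reading the lymphocyte bracket as per µL:

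| Row | SI value | Equivalent (10^3/µL) | Printed bracket | Ratio |
|---|---|---|---|---|
| Platelets HIGH | 500 x 10^9/L | 500 | 100 | 500/100 = 5.0 |
| Lymphocytes HIGH | 4.0 x 10^9/L | 4.0 | 1.5 | 4.0/1.5 = 2.67 |

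Both wrong figures appear elsewhere in the table: 100 is the platelets LOW limit and 1.5 is the neutrophils LOW limit. That suggests a copying slip, and supports taking the SI figure as the intended one.

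**If the brackets were programmed.**

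- Platelets: HIGH is above 100 and LOW is below 100, so every count except exactly 100 x 10^3/µL is PCI.
- Lymphocytes: only counts from 0.8 to 1.5 x 10^3/µL escape both absolute limits. At a white cell count of 8 x 10^9/L, which the absolute white cell limits do not flag, the table's own unflagged band of 22-44% is 0.22 x 8 = 1.76 to 0.44 x 8 = 3.52. All of it exceeds 1.5 and would be HIGH. This holds for any white cell count above 1.5/0.22 = 6.8 x 10^9/L.

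**If the SI values are programmed.** The limits are 500 and 4.0 x 10^9/L, and neither bracket error adds a flag.

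**TSH.** 1 mU/L = 1 µU/mL = 1000 µU/L.

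- HIGH as printed: 5.0/1000 = 0.005 mU/L.
- LOW as printed: 0.5/1000 = 0.0005 mU/L.

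The documents give no TSH range, so one must be assumed. For a normal lower limit from 0.01 to 1 mU/L, the printed HIGH limit lies 0.01/0.005 = 2 to 1/0.005 = 200 times below it, and every normal value is HIGH. If mU/L was intended, a value between 0.005 and 0.5 mU/L, meant to be LOW, would also be called HIGH.

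**The case against.** The best reply is that SI governs in practice. The SI value comes first in each row and the bracket only follows it. SAP 11.2 specifies SI units for the laboratory summaries. Creatinine, fasting glucose, T4, T3 and red cells have SI limits only, so Table 4 cannot be run wholly in conventional units. A reader might infer that Table 4 as printed flags normal platelet and lymphocyte counts. The documents do not support that: it would happen only if someone programmed the brackets, and the platelet result would then look absurd at first output. This part of the reply stands. What remains is that the SI wording is attached to the descriptive statistics and not to the PCI rule, so one sentence is still needed.

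For TSH, a reader might infer that essentially every subject would be flagged. That goes too far as well. It needs an assumed range, and it needs post-baseline TSH values. TSH sits in the biochemistry panel, which is drawn after dosing, but its footnote points to SAP Tables 1 to 3, and none of these has a thyroid row. The documents leave the matter open. They also do not state the intended unit.

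The absent inequality sign on TSH LOW may have been lost in reading the PDF; basophils HIGH and platelets LOW show the same gap. It cannot be counted as an error on this text.

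Finally, the stakes are modest. SAP 2.6 calls the analyses exploratory. Clinical significance is judged by the investigator (Protocol 7.2.2.5 and 8.1.4), and all laboratory results are listed, so a wrong flag could be seen and reversed. This limits the importance of the point but does not make the limits correct.

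**Conclusion.** Table 4 contains two demonstrable unit contradictions, by factors of 5 and 2.7, and a TSH unit that is very probably wrong by a factor of 1000. The platelet and lymphocyte contradictions do harm only if the bracketed figures are used. The TSH limit has no alternative on the page, so as written it would misclassify results, given a normal lower limit between 0.01 and 1 mU/L and TSH measured after baseline. The effect stops at Tables 4.6.3 and 4.6.6 and Listing 8.1.2. The pharmacokinetic analyses and the primary objective are not touched. It should still be corrected, because the errors sit in a rule that will be programmed and the correction is trivial.

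**What to change.** In SAP Table 4:

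1. Set the brackets to 500 x 10^3/µL for platelets HIGH and 4.0 x 10^3/µL for lymphocytes HIGH, to agree with their SI limits.
2. Confirm the intended TSH unit, probably mU/L (the same as µU/mL), and correct both TSH rows. State whether TSH is measured after baseline.
3. Check the comparator on the TSH LOW row against the source document, and those on basophils HIGH and platelets LOW at the same time.
4. Add one sentence to SAP 11.2 saying that the SI values govern PCI programming.

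The cost is a few table cells and one sentence before programming. No data collection, sample size or analysis model changes.

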11.3 Vital Signs

Descriptive statistics for vital signs (systolic and diastolic blood pressure, pulse rate, and body temperature) and their changes from baseline at each post-baseline assessment and at the end of study will be presented by ethnic group and dose. All vital signs will be listed for each subject in the Safety Analysis Set.

Vital sign values will be considered PCI if they meet either the low or high PCI criteria listed in Table 5. The number and percentage of subjects with PCI values at each time point will be tabulated by ethnic group and dose. The percentages will be calculated relative to the number of subjects with baseline and at least 1 post-baseline assessment at that dose level and time point. The numerator is the total number of subjects with at least 1 PCI post-baseline vital sign value at that dose level and time point. A supportive listing of subjects with post-baseline PCI values will be provided including the subject number, ethnic group, dose, baseline, and post-baseline PCI values.

Table 5 Criteria for Potentially Clinically Significant Vital Signs		
Parameter	Classification (on CDRs)	Criteria
Systolic blood pressure (mm Hg)	HIGH and INCREASE	≥ 140 and increase of ≥ 20 from baseline value
	LOW and DECREASE	≤ 90 and decrease of ≥ 20 from baseline value
Diastolic blood pressure (mm Hg)	HIGH and INCREASE	≥ 90 and increase of ≥ 15 from baseline value
	LOW and DECREASE	≤ 50 and decrease of ≥ 15 from baseline value
Pulse rate (bpm)	HIGH and INCREASE	≥ 100 and increase of > 15 from baseline value
	LOW and DECREASE	≤ 45 and decrease of > 15 from baseline value
Temperature	HIGH	$> 38.3^{\circ}\text{C}$ or $> 100.9^{\circ}\text{F}$
	LOW	$< 35^{\circ}\text{C}$ or $< 95^{\circ}\text{F}$

11.4 Electrocardiogram (ECG)

At each timepoint, ECGs are collected in triplicate (any readings after the first three valid readings at a particular timepoint will be considered unscheduled). For numeric ECG variables, the mean of the valid values at each timepoint will be taken. For qualitative ECG results, the worst case will be used. The averages of the ECG triplicate collected predose on Day 1 and predose on Days 4 and 7 (for subjects of Japanese descent) will serve as the subject's baseline ECG for the dose received on that day.

Descriptive statistics for ECG variables (heart rate, PR interval, RR, QRS interval, QT interval, and QTc interval) and their changes from baseline at each assessment time point will be presented by ethnic group and dose. QTc interval will be calculated using both Bazett ($QTcB=QT/(RR)^{1/2}$) and Fridericia ($QTcF=QT/(RR)^{1/3}$) corrections; and if RR is not available, it will be replaced with 60/hr in the correction formula. ECG interpretation will be summarized by visit. A shift table from baseline to each visit for qualitative ECG results will be presented.

Electrocardiogram variables will be considered PCI if the average value for that subject at that time point meets or exceeds the upper limit values listed in Table 6. The number and percentage of subjects with PCI values at each time point will be tabulated by ethnic group and dose. The percentages will be calculated relative to the number of subjects with available baseline and at least 1 post-baseline assessment at that dose level and visit. The numerator is the total number of subjects with at least 1 PCI post-baseline ECG value at that dose level and visit. A listing of all subjects with post-baseline PCI values will be provided including the subject number, ethnic group, dose, baseline, and post-baseline PCI values.

Table 6 Criteria for Potentially Clinically Important ECG Values		
Parameter	Classification (on CDRs)	Criteria
Overall Evaluation	ABNORMAL	Overall Evaluation is ABNORMAL
Heart rate (bpm)	HIGH and INCREASE	≥ 100 and increase of > 15 from baseline value
	LOW and DECREASE	≤ 45 and decrease of > 15 from baseline value
PR interval (msec)	HIGH and INCREASE	≥ 200 and increase of ≥ 20 from baseline value
QRS interval (msec)	HIGH	≥ 120
QTc interval (men) (msec)	HIGH	> 430 and increase from baseline value > 30
QTc interval (women) (msec)	HIGH	> 450 and increase from baseline value > 30

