7.2.2.8 Serology Screen

At the screening visit, a blood sample of approximately 8.5mL will be drawn into a serum separator tube to test for the presence of HIV, HBsAg, and HCV antibody.

The test results must be confirmed negative prior to enrollment in the study. If a test result is positive, the subject will be excluded from entering the study. Results of the virology screen will be reviewed and verified by the study monitor, but will not be collected in the CRF database.

Positive serology results may be reported to the relevant health authorities by study site personnel if required by law.

7.2.2.9 **Electrocardiogram**

Twelve-lead ECGs will be performed at the times specified in [Table 1](#), [Table 2](#), and [Table 3](#). All ECGs will be performed using the equipment supplied by the CRC.

The following parameters will be recorded in the source documentation: heart rate, time elapsed from P wave to R wave in an electrocardiogram (PR), the time between heart beats in an electrocardiogram (RR), measure of time for the 3 main deflections in an electrocardiogram (QRS), and QT intervals along with information on T and U wave morphology (T waves should be captured as normal/abnormal; U waves should be captured as absent/normal or abnormal). The measure of time between the start of the Q wave and the end of the T wave using Bazett's formula in an electrocardiogram (QTcB) and QTcF will be derived from the data in the database. The investigator's assessment of the ECG tracing as normal or abnormal must be documented, and if abnormal, his/her determination of whether the abnormality is clinically significant or not will be documented on the tracing and the source documentation (if different).

The subject should be asked to remove all clothing that covers the location of lead placement. The subject should not have exercised or consumed caffeine within 30 minutes prior to collection. The subject must be resting in the supine position for at least 5 minutes prior to collecting the ECG.

In some cases, it may be appropriate to repeat abnormal ECGs to rule out improper lead placement as contributing to the ECG abnormality. It is important that leads are placed in the same positions each time in order to achieve precise ECG recordings.

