Triplet ECG recordings, including a 10-second rhythm strip, should be taken at each time point. They should be immediately assessed as valid recordings and if not valid, they should be repeated. Invalid recordings will not be entered included in the CRF database.

A triplicate ECG recording is to be performed at each time point approximately 2-4 minutes apart. The averages of the ECG triplicate collected predose on Day 1 (all subjects) and predose on Days 4 and 7 (subjects of Japanese descent) will serve as the subject's baseline ECG.

To ensure safety of the subjects, a qualified individual at the investigator site will make comparisons to baseline measurements.

If the triplicate average QTcF interval (calculated online on site) is increased by >45 msec from the baseline or an absolute QTcF value is >500 msec for any scheduled ECG, then 2 additional ECGs will be collected, approximately 2-4 minutes apart, to confirm the original measurement. If either of the QTcF values from these repeated ECGs remains above the threshold value (>45 msec from the baseline; or is >500 msec), then a single ECG must be repeated at least hourly until QTcF values from 2 successive ECGs fall below the threshold value that triggered the repeat measurement. When triplicate ECGs are collected, the mean of the triplicate measurements should be used to trigger the decision to collect follow-up ECGs.

If QTcF values remain above 500 msec (or >45 msec from the baseline) for >4 hours (or sooner at the discretion of the investigator) or QTcF intervals get progressively longer, the subject

should undergo continuous ECG monitoring. A cardiologist should be consulted if QTcF intervals do not return to <500 msec (or to <45 msec above the baseline) after 8 hours of monitoring (or sooner at the discretion of the investigator).

If a machine-read QTcF value is prolonged, as defined above, repeat measurements may not be necessary if a qualified physician's interpretation determines that the QTcF values are in the acceptable range.

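### SAP Table 6 counts an ECG abnormality already present at baseline as PCI, and its QTc rows can miss a QTcF rise above 45 msec when the post-dose value stays at or below 430 msec (men) or 450 msec (women)

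*SAP*

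**What the plan says.** SAP 11.4 and Table 6 define the ECG PCI criteria.

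- **Overall evaluation.** The only condition is "Overall Evaluation is ABNORMAL". There is no reference to baseline or to clinical significance. On combining the three tracings the SAP says: "For qualitative ECG results, the worst case will be used".
- **QTc.** For men the criterion is "> 430 and increase from baseline value > 30"; for women it is "> 450 and increase from baseline value > 30". Level and rise must both be met. The rows say only QTc, although SAP 11.4 computes both QTcB and QTcF.
- **Other rows.** Heart rate and PR also combine a level with a change from baseline. QRS uses a level alone.
- **Counting.** Subjects with at least one PCI value are counted by ethnic group and dose (Table 4.8.4) and listed (Listing 8.3.2). Under SAP 18.3, repeat assessments also count towards PCI.

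Protocol 7.2.2.9 calls for two further ECGs when the triplicate mean QTcF "is increased by >45 msec from the baseline or an absolute QTcF value is >500 msec". If the finding is confirmed, ECGs are repeated at least hourly, and continuous monitoring follows if it persists. For an abnormal tracing, the protocol also says that "his/her determination of whether the abnormality is clinically significant or not will be documented".

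**The concern.** ECG change is a listed safety endpoint (Protocol 9.9.1), and the two ethnic groups are to be compared directly at 100 µg (Protocol 9.9.2). The PCI table is where a reader will look for the number of subjects with a notable ECG finding.

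Two features work against that use. A stable abnormality present before dosing is counted as if it had arisen after it. And a subject whose QTcF rise set off the protocol's own repeat-ECG procedure may not appear on QTc grounds in either the PCI table or the PCI listing.

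**Working it through.** The documents give no figure to reproduce here. The check compares the rules as written.

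**1. Overall-evaluation row.** Take a subject judged abnormal predose and abnormal, with the same finding, at the 24 h ECG.

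- Heart rate, PR and QTc rows: no change, so not PCI.
- Overall-evaluation row: abnormal post-dose, so PCI.

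A Caucasian subject receives one dose and would be counted at 100 µg. A Japanese subject would be counted at 100, 25 and 50 µg. Follow-up results are placed under 100 µg (SAP 11), so the same finding at that visit counts there too.

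Size per subject: 1/12 = 8.3 percentage points; 2/12 = 16.7 points. The documents give no frequency of stable abnormalities in volunteers screened as healthy. If it were 10% to 30% (assumption), the expected number per group would be 12 × 0.10 = 1.2 to 12 × 0.30 = 3.6.

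**2. QTc rows against the protocol trigger.** Let B be baseline and R the rise, in msec, with Table 6 applied to QTcF.

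- Protocol trigger: R > 45, or B + R > 500.
- Table 6: B + R > L and R > 30, with L = 430 (men) or 450 (women).

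A rise above 45 always meets the 30 msec condition, so it is missed only if B + R ≤ L. With R > 45 this requires B < L − 45:

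- men: B < 430 − 45 = 385;
- women: B < 450 − 45 = 405.

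| Case | Rise | Protocol trigger | Table 6 |
|---|---|---|---|
| Man, 375 to 425 | 50 | yes | no |
| Woman, 395 to 445 | 50 | yes | no |
| Man, 385 to 431 | 46 | yes | yes |
| Man, 400 to 435 | 35 | no | yes |
| Woman, 420 to 455 | 35 | no | yes |

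The largest unflagged rise is L − B: 60 msec for a man at 370 (430 − 370) and 60 msec for a woman at 390 (450 − 390). The last two rows of the table show the opposite case, where Table 6 is the stricter rule.

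**3. The 500 msec limb.** A value above 500 escapes Table 6 only if R ≤ 30, so B must exceed 500 − 30 = 470. That is unlikely given the 450 msec QTcF limit at screening.

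**4. How many baselines fall in the gap.** The documents give no baseline QTcF distribution. Assuming normality with mean 390 to 420 and SD 15 to 20 msec, the share below the cut is Φ((385 − mean)/SD) for men and Φ((405 − mean)/SD) for women:

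- men: from Φ((385 − 420)/15) = 0.01 to Φ((385 − 390)/20) = 0.40;
- women: from Φ((405 − 420)/15) = 0.16 to Φ((405 − 390)/15) = 0.84.

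These are shares of subjects in whom a rise above 45 msec could be missed. They are not rates of missed events; the documents give no frequency of such rises.

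**The case against.** The strongest case against is that nothing is lost. SAP 11.4 plans change-from-baseline statistics for QTcB and QTcF, and SAP 18.1 includes the maximum by default, so a 50 msec rise would show in Table 4.8.1. The shift table (4.8.3) separates new from unchanged abnormalities. The PCI listing gives baseline beside post-baseline values, and Listing 8.3.1 gives every ECG with the investigator's interpretation. Clinically significant ECG changes are adverse events under Protocol 8.1.4. SAP 2.6 calls the statistical analyses exploratory.

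Most of this stands and limits the weight of the point. It does not correct the outputs at issue. A maximum shows the largest change, not how many subjects passed the trigger. A shift table elsewhere does not remove unchanged findings from the PCI count.

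Four stronger readings are tempting, and the documents do not support them.

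- **Table 6 misses QTcF rises above 45 msec in general.** It misses them only in the baseline range derived above.
- **The SAP contradicts the protocol.** One rule is an on-site trigger for repeat ECGs and the other a tabulation rule. They are not aligned, but they can coexist.
- **PCI counts would mainly reflect benign variants.** Table 6 lists criteria by parameter, and nothing says that the rows are pooled. The table shells are in a separate document.
- **The overall-evaluation row should require clinical significance.** That would drop new abnormalities judged not significant from a screen for potentially important values. The protocol has significance recorded on the tracing and in source documents; whether it reaches the database is not stated.

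**Conclusion.** Both parts hold on the text, within limits. The overall-evaluation row counts abnormalities already present at that dose's baseline, at 8.3 percentage points per subject in a group of 12. The QTc rows can miss a QTcF rise above 45 msec, but only for baselines below 385 msec (men) or 405 msec (women); once the post-dose value passes 430 or 450 msec they flag more than the protocol trigger does.

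The boundaries are exact arithmetic from the two documents, provided that Table 6 is applied to QTcF, which it does not state. The shares of subjects in the gap (about 1% to 40% of men, 16% to 84% of women) and the frequency of stable abnormalities rest on assumptions. The consequence is confined to who appears in Table 4.8.4 and Listing 8.3.2. It does not touch the PK objectives. The change is worth making because it is cheap, not because the safety data would otherwise be hidden.

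**What to change.** In SAP Table 6:

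- **(a)** Restrict the overall-evaluation row to subjects who are abnormal post-dose and were not abnormal at that dose's baseline. Do not add a clinical-significance condition; show the investigator's significance judgement in the listing if it is in the database.
- **(b)** Reconcile the table with Protocol 7.2.2.9 by adding the protocol's own triggers as two tabulation rows on the triplicate-mean QTcF: increase above 45 msec from baseline, and value above 500 msec. Keep the existing QTc rows and state whether they use QTcB or QTcF.

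With (b), no QTcF value that meets the protocol trigger on the triplicate mean can be absent from the PCI table. With (a), unchanged baseline abnormalities leave the count.

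The cost is SAP wording, some programming on ECG data already in the planned outputs, and two more rows in Table 4.8.4. No clinical procedure changes, and the added rows imply no view on which threshold is clinically right.
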